APPENDIX D: STUDY DEFINITIONS

American Society of Anaesthesiologists (ASA) Classification

ASA Classification [21]	Definition	Example
I	A normal healthy patient	Healthy, non-smoking, no or minimal alcohol use
II	A patient with mild systemic disease	Mild diseases only without substantive functional limitations. Current smoker, social alcohol drinker, pregnancy, obesity (30<BMI<40), well-controlled DM/HTN, mild lung disease
III	A patient with severe systemic disease	Substantive functional limitations; One or more moderate to severe diseases. Poorly controlled DM or HTN, COPD, morbid obesity (BMI ≥40), active hepatitis, alcohol dependence or abuse, implanted pacemaker, moderate reduction of ejection fraction, ESRD undergoing regularly scheduled dialysis, history (>3 months) of MI, CVA, TIA, or CAD/stents
IV	A patient with severe systemic disease that is a constant threat to life	Recent (<3 months) MI, CVA, TIA or CAD/stents, ongoing cardiac ischemia or severe valve dysfunction, severe reduction of ejection fraction, shock, sepsis, DIC, ARD or ESRD not undergoing regularly scheduled dialysis
V	A moribund patient who is not expected to survive without the operation	Ruptured abdominal/thoracic aneurysm, massive trauma, intracranial bleed with mass effect, ischemic bowel in the face of significant cardiac pathology or multiple organ/system dysfunction

Clinical Frailty Scale

Clinical frailty scale [22] (nine components):

1. **Very Fit:** People who are robust, active, energetic, and motivated.
2. **Well:** People who have no severe disease symptoms but are less fit than category 1. They exercise or are very active occasionally, e.g., seasonally.
3. **Managing Well:** People whose medical problems are well-controlled but are not regularly active beyond routine walking.
4. **Living With Very Mild Frailty:** While not dependent on others for daily help, symptoms often limit activities. A common complaint is being "slowed-up" and being tired during the day.
5. **Living with Mild Frailty:** These people usually have more evident slowing and need help in higher-order instrumental activities of daily living (IADLs) such as finance, transportation, heavy housework, and medication management. Typically, mild frailty progressively impairs shopping and walking outside alone, meal preparation, and housekeeping.
6. **Living With Moderate Frailty:** People need help with all outside activities and housekeeping. Inside often have problems with stairs, need help with bathing, and may need minimal assistance with dressing.
7. **Living With Severe Frailty:** Completely dependent for cognitive and physical personal care. However, they seem stable and not at high risk of dying (within six months).
8. **Living with Very Severe Frailty:** Completely dependent for personal care and approaching end of life. Typically, they could not recover even from minor illnesses.
9. **Terminally Ill:** Approaching the end of life. This category applies to people with a life expectancy of under six months who are not otherwise living with severe frailty.

Indication for Surgery

Indication	Definition
Biliary colic	The presence of colicky right upper quadrant pain associated with gallstones or sludge on an USS, but no signs of acute cholecystitis [23]
Acute calculous cholecystitis	Clinical (right upper quadrant pain, with or without fever, WCC > 11 × 10 ⁹ /l) OR ultrasound evidence (thick walled gallbladder (≥ 3mm), OR USS tenderness over the gallbladder, the presence of gallstones) [23,24]
Acute acalculous cholecystitis	Clinical OR ultrasound evidence (thick walled gallbladder and/or pericholecystitis, USS tenderness over the gallbladder) in the absence of gallstones [23]
Chronic calculous cholecystitis	Previous clinical or ultrasound evidence (thick walled gallbladder and/or pericholecystitis, OR USS tenderness over the gallbladder OR the presence of gallstones) of cholecystitis [23]
Common bile duct stone	Common bile duct stones, as confirmed by before or at the time of surgery
Gallbladder polyp	Hyperechoic lesions on USS imaging which have no acoustic shadow and do not move with positional changes, with no overt features of malignancy [25]
Dyskinesia	Biliary like abdominal pain, occurring in a normal appearing gallbladder with a functional HIDA scan showing an abnormal gallbladder ejection fraction of less than 40% [26,27]

Tokyo Guidelines 2018 for Grading of Acute Cholecystitis

Tokyo guidelines 2018 grading [24] are listed below:

- **Grade I (mild):** No organ dysfunction and mild inflammatory changes in the gallbladder.
- **Grade II (moderate):**
 - Elevated WBC count (>18,000/mm³)
 - Palpable tender mass in the right upper abdominal quadrant
 - Duration of complaints >72 hours
 - Marked local inflammation (gangrenous cholecystitis, pericholecystic abscess, hepatic abscess, biliary peritonitis, emphysematous cholecystitis)
- **Grade III (severe):**
 - Cardiovascular dysfunction: hypotension requiring treatment with dopamine ≥5 µg/kg per min, or any dose of norepinephrine
 - Neurological dysfunction: decreased level of consciousness
 - Respiratory dysfunction: PaO₂/FiO₂ ratio <300
 - Renal dysfunction: oliguria, creatinine >2.0 mg/dl
 - Hepatic dysfunction: PT-INR >1.5
 - Hematological dysfunction: platelet count <100,000/mm³

Revised Atlanta Criteria for Acute Pancreatitis

Atlanta Criteria [28] is listed below:

- **Mild:** No organ failure. No local complications (e.g., necrosis or collection). No systemic complications.
- **Moderate:** Transient organ failure (<48 hours) OR Local/systemic complications
- **Severe:** Persistent organ failure

Urgency of Surgery

The urgency of index cholecystectomy is defined as [3]:

- **Elective:** planned elective admission for cholecystectomy via a routine surgical waiting list from the outpatient department only. Patients on an elective waiting list treated as an emergency should be classed as ‘acute’ cases.
- **Delayed:** all other planned cholecystectomies; for example, patients who have had one or more acute admissions with biliary symptoms, but then discharged for a planned procedure on an elective operating list.
- **Emergency:** emergency admission with biliary disease through the Emergency Department or primary care, and cholecystectomy performed during that emergency admission.

Nassar Grade of Operative Difficulty

[figure not shown]
Grade [29]	Gallbladder	Cystic pedicle	Adhesions
I	Floppy, non-adherent	Clear, thin	Simple, up to neck and Hartmann’s pouch
II	
 • Mucocele • Packed with stones 	Fat-laden	Simple, up to the body
III	
 • Deep fossa • Acute cholecystitis • Contracted, fibrous Hartmann’s pouch adherent to CBD or with stone impaction 	
 • Abnormal anatomy • Cystic duct short, dilated or obscured 	
 • Dense, up to the fundus • Involving hepatic flexure or duodenum
IV	
 • Completely obscured • Empyema/gangrene • Mass 	Impossible to clarify	Dense, fibrous, wrapping the gallbladder. Duodenum or hepatic flexure is difficult to separate
V	As in grade IV with presence of Mirizzi Syndrome type 2 or higher, cholecysto-cutaneous, cholecysto-duodenal or cholecysto-colic fistula		

Clavien-Dindo Classification System

Grade [30]	Definition (examples listed in italics)
I	
Any deviation from the normal postoperative course without the need for pharmacological (other than “allowed therapeutic regimens”), surgical, endoscopic or radiological intervention.
 
Allowed therapeutic regimens are: selected drugs (antiemetics, antipyretics, analgesics, diuretics and electrolyte replacement), physiotherapy and wound infections opened at the bedside but not treated with antibiotics.
 
Examples: Ileus (deviation from the norm); hypokalaemia treated with K; nausea treated with cyclizine; acute kidney injury treated with intravenous fluids.

II	
Requiring pharmacological treatment with drugs beyond those allowed for grade I complications. Blood transfusions and total parenteral nutrition are also included.
 
Examples: Surgical site infection treated with antibiotics; myocardial infarction treated medically; deep venous thrombosis treated with enoxaparin; pneumonia or urinary tract infection treated with antibiotics; blood transfusion for anaemia.

IIIa	
Requiring surgical, endoscopic or radiological intervention, not under general Anaesthetic (GA).
 
Examples: Therapeutic endoscopic therapy (do not include diagnostic procedures); interventional radiology procedures.

IIIb	
Requiring surgical, endoscopic or radiological intervention, under GA.
 
Examples: Return to theatre for any reason.

IVa	
Life-threatening complications requiring critical care management with single organ dysfunction, or neurological complications including brain haemorrhage and ischemic stroke (excluding TIA).
 
Examples: Single organ dysfunction requiring critical care management, e.g. pneumonia with ventilator support, renal failure with filtration; SAH; stroke

IVb	
Life-threatening complications requiring critical care management with multi-organ dysfunction.

V	
Death

Definition of Complications

Complication	Definition
Surgical site infection	Purulent drainage from the incision; OR At least two of: pain or tenderness; localised swelling; redness; heat; fever; AND the incision is opened deliberately to manage infection, or the clinician diagnoses a surgical site infection; OR Wound organisms AND pus cells from aspirate/ swab.
Pulmonary complications [31]	Atelectasis OR pneumonia OR pulmonary aspiration OR acute respiratory distress syndrome
Bile leak	Grade A: bile leak which requires little or no change in the patient's management; resolves with conservative management within 1 week. Grade B: bile leak or collection which requires additional diagnostic or interventional procedures, such as ERCP or re-laparoscopy or Grade A bile leak which lasts more than 1 week. Grade C: Bile leak or collection which requires re-laparotomy.
Intra-abdominal abscess/collection	A clinical diagnosis of intra-abdominal collection (fever or abdominal pain or wound infection with dehiscence of any layer below fat/Scarpa's fascia) with operative or radiological evidence of a collection.
Acute pancreatitis [28]	Diagnosed using the revised Atlanta guidelines which state the diagnosis of acute pancreatitis requires two of the following three features: 
 Abdominal pain consistent with acute pancreatitis (acute onset of a persistent, severe, epigastric pain often radiating to the back) Serum lipase activity (or amylase activity) at least three times greater than the upper limit of normal Characteristic findings of acute pancreatitis on contrast-enhanced computed tomography.
Common bile duct injury [32-34]	Any injury to the main biliary tree will be classified using the Strasberg Classification System (see figure below): A – leak from cystic duct or small duct in liver bed B – occlusion of an aberrant right hepatic duct C – leak from an aberrant right hepatic duct D – lateral injury to the common hepatic or bile duct (<50% of circumference) E1 – transection or stricture of common hepatic or common bile duct >2cm from the hilum. E2 - transection or stricture of common hepatic duct <2cm from the hilum. E3 – Transection of the common hepatic duct at the level of the bifurcation without loss of contact between left and right hepatic duct. E4 – Transection of the common hepatic duct at the level of the bifurcation with loss of communication between the left and right hepatic duct. E5 – injury of a right segmental duct combined with an E3 or E4 injury.

Strasberg Classification System

American Joint Committee on Cancer (AJCC) 8th Edition TNM Stage

Category [35]	Definition
T category	
Tis	Carcinoma in-situ
T1a	Limited to the lamina propria
T1b	Invades the muscle layer
T2a	Invades the perimuscular connective tissue on the peritoneal side

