- **Return to theatre:** Each patient should only be entered into the study once. Any patient returning to theatre and requiring a cholecystectomy for whatever indication, should not be included.
- **Known gallbladder malignancy:** when the diagnosis of gallbladder cancer is established pre-operatively, the patient should be excluded. However, if gallbladder cancer is found unexpectedly during or after cholecystectomy (i.e. on histology), the patient should be included.

STUDY PROCEDURES

Site Survey

In order to describe local processes and resources, each site will be asked to complete an online site survey questionnaire to delineate the variation of cholecystectomy services and training amongst included hospitals (**Appendix C**).

*Completion of the short site survey can be done by a supervising consultant (preferred) or a hospital lead trainee that is familiar with the cholecystectomy practices at your site. Completion of the site survey is necessary before the site is granted access to the online **GECKO**: Data Collection form.*

Data Collection

Collaborators will collect data on consecutive eligible patient undergoing cholecystectomy within the pre-specified data collection periods (**Table 1; page 15**). Data collectors should use a combination of the **GECKO** Case Report Form (**Appendix A**) alongside the Data Dictionary (**Appendix B**) to successfully record required data on all eligible patients. Collaborators will create clear mechanisms appropriate to their institution to identify and include all eligible patients, involving daily review of operating logbooks, multidisciplinary team meeting, admission and handover lists. Local arrangements may include daily review of the patient and notes focused on included data points.

Data will be collected and stored online via the Research Electronic Data Capture (REDCap) web application (**see pages 20-21**), hosted and managed by the University of Edinburgh, United Kingdom. No patient identifiable data will be uploaded or stored on the REDCap database.

Strategies to identify consecutive eligible patients could include:

- *Daily review of elective theatre lists.*
- *Daily review of handover sheets/emergency admission and ward lists.*
- *Daily review of theatre logbooks (both elective and emergency).*

Follow-up Period

Centres will undertake patient follow-up at two timepoints:

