The secondary endpoints include:

- Rates of achieving a critical view of safety.
- Rates of different bailout procedures initiated when safe cholecystectomy is compromised.
- 30-day and one-year rates of textbook outcomes [2] for cholecystectomy, which covers: postoperative complications (Clavien-Dindo classification), intraoperative complications (including bile duct and vascular injuries), length of stay, readmission, mortality, and postoperative imaging or intervention.
- Unsuspected gallbladder cancer rates and their 30-day and one-year outcome rates, which includes: (1) complication rates (Clavien-Dindo classification); (2) time-to-recurrence rates (time from surgery to recurrence); and (2) revisional surgery rates (liver resection, bile duct resection and/or lymph node dissection).
- A description of the global variation in the availability of cholecystectomy services, training and sustainable practice.

Control of Bias and Confounding

Data will be collected on audit standards and confounding factors for risk-adjusted analyses. These include age, sex, body mass index, American Society of Anaesthesiologists (ASA) grade, and relevant comorbidities. Variables including operative urgency, operative contamination, and operative approach will also be collected. Without appropriately adjusting for risk factors, it is likely that any findings would be biased and unable to be appropriately analysed on an international scale. A full list of required data fields is available in **Appendix B**, and on the REDCap database.

Data Analysis & Sample Size

Variation across different international health settings will be tested using the human development index (HDI) countries [17] a composite statistic of life expectancy, education and income indices published by the United Nations. Initially, data will be reported using descriptive analyses. Comparisons between groups will be undertaken using appropriate parametric and non-parametric analyses. Multilevel logistic regression multivariate models will be constructed to account for case mix, with population stratification by hospital and country as random effects.

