8. Operation performed	Standard total cholecystectomy Total cholecystectomy by the fundus-first (top down) approach Subtotal cholecystectomy (reconstituting / fenestrated) Not performed (diagnostic laparoscopy / cholecystostomy) Definitions of subtotal cholecystectomy: 
 Fenestrated: does not occlude the gallbladder but may suture the cystic duct internally Reconstituting: closes off the lower end of the gallbladder, creating a remnant gallbladder
9. Abdominal drain insertion	Yes / No
10. Anatomical Biliary variant	Yes / No
11. Intraoperative CBD Assessment	Intraoperative cholangiogram (IOC) / Incisionless fluorescent cholangiography/ Laparoscopic ultrasound / Intraoperative ERCP If yes to any of the above: 
 Decision: Selective / Routine. If selective, state Indication: Raised liver function test / Concern of a bile duct injury / pre-operative imaging suggestive of CBD stone Findings: Stone / No stone. If stone, tick all that apply for management: Flushing with saline and smooth muscle relaxant / Fogarty catheter trawl / Basket retrieval / Choledochoscope / No intraoperative treatment attempted
12. Common Bile Duct exploration	Yes (Trancystic / Choledochotomy) / No If Choledochotomy then select closure: Primary closure / T-tube
13. Operative contamination	Clean (Gastrointestinal (GI) and genitourinary (GU) tract not entered) Clean-Contaminated (GI or GU tracts entered but no gross contamination) Contaminated (GI or GU tracts entered with gross spillage or major break in sterile technique) Dirty (There is already contamination prior to operation, e.g., faeces or bile).
14. Intraoperative complications - excluding bile duct injury (BDI) (Select all that apply)	Bile spilt / Stones Spilt / Bleeding / Major vascular injury / Bowel injury
15. Were reusable gowns used in this procedure?	Yes (All scrubbed staff/ some scrubbed staff) / No
16. Were reusable drapes used in this procedure?	Yes / No
30-day Outcomes	Required data (definition / comment)
1. Highest 30-day Clavien-Dindo (CD) Grade	0 / I / II / IIIa / IIIb / IVa / IVb / V (Appendix D for definitions) If CD IIIa: Radiological drainage (yes / No) If CD IIIb: Re-laparoscopy (yes / No) If CD V (death): please indicate time from index cholecystectomy to death: number of days (whole number, 0 = same day)

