2. Unplanned critical care admission - where critical care admission was not part of pre-operative plan	Yes / No If yes, please indicate length of stay in critical care: number of days (whole number)
3. Unplanned Re-imaging - where imaging in post-operative period (e.g.,	Yes / No If yes then tick all that apply: USS / CT / MRI / ERCP

CT, MRCP) was not part of pre-operative plan
	

4. 30-day postoperative complications (Select all that apply)
	
Surgical site infection (CD Grade* 0 / I / II / IIIa / IIIb / IVa / IVb / V) Postoperative pulmonary complications (CD Grade* 0 / I / II / IIIa / IIIb / IVa / IVb / V) Bile leak (CD Grade* 0 / I / II / IIIa / IIIb / IVa / IVb / V) Bleeding (CD Grade* 0 / I / II / IIIa / IIIb / IVa / IVb / V) Intra-abdominal collection (CD Grade* 0 / I / II / IIIa / IIIb / IVa / IVb / V) Acute pancreatitis (CD Grade* 0 / I / II / IIIa / IIIb / IVa / IVb / V) *For all of the above, please indicate the Clavien-Dindo grade associated with that complication

5. Length of stay
	
Whole number of days (Where discharge < 23 hours, enter 0. If the patient has not been discharged prior to the end of 30-day follow-up, enter '31')

6. Unplanned readmission within 30 days
	
Yes (Length of stay) / No

Bile Duct Injury (BDI) data fields
	
Required data (definition / comment)

1. BDI identified within 30-days of index cholecystectomy
	
Yes / No If yes: please fill in the rest of the data points below. If No: Was BDI identified within one-year of index cholecystectomy: Yes / No (if yes, then please fill in the rest of the data points below)

2. Presentation of BDI
	
Intraoperatively / Controlled bile leak from surgically placed abdominal drain / Abdominal pain due to uncontrolled bile leak / Obstructive jaundice or cholangitis / Intra-abdominal abscess or biloma

3. Days from index cholecystectomy to diagnosis
	
Number of days (0 = intraoperatively)

4. Bile duct injury grade
	
A / B / C / D / E1 / E2 / E3 / E4 / E5 (Strasberg Injury Grade: Appendix D for definition)

5. Concomitant vascular injury
	
Yes (Right hepatic artery / Common hepatic artery / Main portal vein / Right portal vein) / No

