
6. Imaging modality to investigate and confirm BDI
	
On-table cholangiography (OTC) / USS / MRCP / CT / ERCP / Percutaneous transhepatic cholangiography (PTC) / Nuclear medicine scan (e.g. Functional liver scan) / Tubogram / None

7. Discussion with a specialist HPB centre
	
Yes / No / Not required (Injury occurred at specialist HPB centre) If yes:
 
 Transferred to specialist HPB centre: Yes / No Time from injury to referral: number of days (whole number)

8. Management of Bile duct injury (Select all that apply)
	
Non-surgery (ERCP only / ERCP and stent / PTC) / Surgery (washout only / repair) If any of the above:
 
 Time after index cholecystectomy: number of days (Whole number, day of index cholecystectomy = day 0) 
If surgical repair:
 
 Specialty of surgeon performing Bile duct injury repair: HPB surgeon / UGI surgeon / General surgeon Method of repair: Roux-en-Y Hepaticojejunostomy / CBD repair without T-tube / CBD repair with T-tube / CBD end to end anastomosis / Hepaticoduodenostomy Vascular repair: Yes / No One-year complications: Stricture formation / Cholangitis / anastomotic leakage / intra-abdominal abscess or biloma / re-repair. If yes to any, time from repair to complication: number of days (Whole number, day of repair = day 0)

	Stricture definition: defined as a clinically relevant stricture leading to either jaundice, significant alterations of the liver function tests, cirrhosis or reoccurring cholangitis requiring radiological/surgical intervention or a liver failure related death
Histology data fields	Required data (definition / comment)
1. Postoperative histology	
Not sent for examination / Sent for examination
 
If sent for examination, please complete:
 
 • Indication: Routine / Selective • Time from index cholecystectomy to histology result: Number of days (whole number) • Result: Benign / Malignant 
If Malignant, please complete the rest of the data points below

2. Staging investigations after index cholecystectomy (select all that apply)	
CT thorax abdomen pelvis / MRI liver / PET-CT / Staging laparoscopy
 
For any of the above, please indicate time from histology result to staging investigation: number of days (whole number)

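### The grade IIIb example in Appendix D makes a planned re-resection for unsuspected gallbladder cancer a complication, although the protocol lists complications and revisional surgery as separate outcomes

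*Protocol*

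**What the plan says.** Appendix D (Clavien-Dindo Classification System) defines IIIb as intervention under general anaesthetic and gives sites one example: "Return to theatre for any reason". The Section 6 form in Appendix A and the one-year fields in Appendix B ask for the highest grade reached within a year of the index operation.

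The Exclusion Criteria remove known gallbladder cancer but keep the unexpected cases: "However, if gallbladder cancer is found unexpectedly during or after cholecystectomy (i.e. on histology), the patient should be included". For these patients, Secondary Outcome Measures lists Clavien-Dindo complication rates and revisional surgery rates (liver, bile duct or nodal) as distinct 30-day and one-year outcomes. Revisional surgery also has its own histology fields: whether done, type, and days from the histology result.

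Unplanned re-imaging is a 30-day field in Appendix B. It covers postoperative imaging that was outside the pre-operative plan, with the instruction "If yes then tick all that apply: USS / CT / MRI / ERCP". Among the answers for a duct stone found at surgery is "No intraoperative treatment attempted".

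**The concern.** Two outcomes that the protocol means to report side by side overlap by definition. A patient whose cancer is found on histology and who then has a planned liver-bed or nodal resection is counted once under revisional surgery and, on the literal wording, again as having a IIIb complication of the cholecystectomy. The cancer complication rate would then partly measure how often re-resection was done. If collectors differ in how they read the example, the rate would also reflect reading habits across sites. Collectors include medical students and nurses at an anticipated 500 or so centres, so differing readings are plausible.

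The re-imaging field raises a similar but weaker problem. Staging for a cancer that nobody suspected cannot have been in the pre-operative plan, so a staging CT or MRI within 30 days meets the definition of unplanned.

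**Working it through.** **Wording.** No arithmetic is needed for the core point.

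1. Only unsuspected cancers are in the cohort, so any re-resection is decided after the index operation.
2. A re-resection under general anaesthetic is a return to theatre and meets the IIIb definition and its example. No section exempts planned oncological surgery.
3. The one-year field takes the highest grade, so the re-resection sets the grade at IIIb unless something worse occurs.
4. The IIIb sub-question on the form in Appendix A asks whether there was a re-operation, not why.
5. A staging laparoscopy, one of the listed options ("CT thorax abdomen pelvis / MRI liver / PET-CT / Staging laparoscopy"), would be graded the same way if done under general anaesthetic.

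**Size.** The protocol gives no figure to reproduce. Only the sample of about 15,000 comes from it; the rates below are assumptions.

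- Cancer rate 0.2% to 0.5%: 15,000 × 0.002 = 30 and 15,000 × 0.005 = 75 patients.
- Share revised r = 40%; true rate of IIIb or worse c = 10%; the two independent.
- Recorded rate if every site codes literally: 1 − (1 − r)(1 − c) = 1 − 0.60 × 0.90 = 46%, against 10%.
- If only half of the re-resections are coded literally: 1 − (1 − 0.20)(0.90) = 28%.
- Newly misgraded patients: r × (1 − c) × n = 0.40 × 0.90 × 30 = 10.8, and 0.40 × 0.90 × 75 = 27, so about 11 to 27. The full 40% would be 12 to 30, but a tenth of those are already IIIb or worse and are not newly misgraded.
- Whole cohort: 10.8/15,000 = 0.07 points to 27/15,000 = 0.18 points.

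**Range.** With c = 5% and r from 20% to 60%, the recorded rate runs from 1 − 0.80 × 0.95 = 24% to 1 − 0.40 × 0.95 = 62%. Even with a 1% cancer rate (150 patients) and r = 60%, the cohort effect is 0.60 × 0.95 × 150 = 85.5 patients, or 0.57 points.

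**Re-imaging.** The sole exemption is the pre-operative plan. Staging CT or MRI within 30 days therefore counts, as would an ERCP within 30 days that was decided at the index operation for a stone left in place. Section 6 has no one-year re-imaging field, so later scans are not captured there. Diagnostic scans are not Clavien-Dindo complications.

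**The case against.** The strongest reply is that the phrase is an example, not the rule. Clavien-Dindo grades complications, and an experienced collector may well not grade planned oncological surgery at all. That stands as far as it goes: the 46% is an upper figure that needs literal coding everywhere. But the example puts no limit on the reason for returning, so the reply shows that coding may vary, not that the problem is absent.

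A second reply is that the overlap can be untangled in analysis, because revisional surgery has its own fields and each listed complication carries its own grade. This is partly right, and an analysis plan may provide for it. Recovery is incomplete, because the list of complications is not exhaustive and the form does not ask why the patient returned to theatre.

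Some stronger readings are tempting, but the protocol does not support them:

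- *Every stone left in place becomes a IIIa complication and a textbook-outcome failure.* The IIIa example ("Therapeutic endoscopic therapy (do not include diagnostic procedures); interventional radiology procedures") exempts only diagnostic procedures. However, the stone field does not say that an ERCP follows, that it is therapeutic, or that it was decided at surgery. The protocol gives neither the grade threshold nor the field mapping for the textbook outcome.
- *Centres that re-resect will be reported as worse.* At 15,000/500 = 30 patients per centre and the assumed 0.2% to 0.5%, a centre has 0.06 to 0.15 cancers, and hospital-specific performance is not to be reported.
- *The distortion follows HDI.* The site survey allows histology practice to vary, but nothing in the protocol shows that it varies with HDI.
- *Complications of the second operation should not count.* A one-year complication rate in cancer patients may legitimately include them.

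**Conclusion.** The point holds for the cancer complication outcome. As worded, the IIIb example makes a planned re-resection under general anaesthetic a complication; if sites depart from that wording unevenly, coding is inconsistent. On the assumed rates (40% revised, true 10% at IIIb or worse, independent, literal coding throughout), the recorded rate rises from 10% to 46%, about 11 to 27 newly misgraded patients among 30 to 75. That dominates the subgroup result. It moves the whole-cohort rate by less than 0.2 points on these rates and does not affect compliance with the audit standards, the primary endpoint.

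The re-imaging point is secondary and less certain. The definition does sweep in early staging and an ERCP already decided at the index operation. Whether that fails the textbook outcome depends on a definition that the protocol does not give.

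**What to change.** - In Appendix D, change the IIIb example to: *return to theatre to treat a complication*.
- State there and in Appendix B that revisional oncological surgery is recorded in its own fields and is not itself graded as a complication. Complications of that surgery may still be graded, with a flag saying so.
- In the re-imaging field of Appendix B, exempt cancer staging, and imaging or ERCP already decided by the end of the index operation. One tick box can record this.
- If data collection has closed, report the cancer complication rate with and without patients whose only IIIb event could be the revisional operation, and state the limitation.

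The cost is a few lines of wording and one tick box, with no change to patient care. The small downside is slightly less comparability with series that count every return to theatre; reporting both versions would deal with it.
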